Decreasing Sedentary/Increasing Physical Activity for Parents and Children Praising & Ignoring/ Making Healthy Choices	Family Exercise Ideas and Cooking with a Limited Budget Parties, Bar-B-Qs, and Eating Out	Increased information on exercise activities for children that can be done alone (due to poor proximity to neighbors, etc.)
Monitoring Screen Time	Nutrient Density	Increased attention to self- esteem
Portion Sizes/Healthy Foods in the Home	Self-Esteem	Tips for dressing appropriately for larger body types

monthly intervention sessions, for a total intervention period of 8 months (to coincide with the length of the typical school year).

Intervention groups will be delivered weekly to family homes at times that are convenient for participating families (typically evenings and weekends). If a participating family misses one group session, they will receive a makeup phone call. The 8 parent/child pairs from

each school will meet together via technology in a single cohort from their homes with intervention staff and meetings will last about one hour. The intervention focuses on behavioral, nutrition, and exercise topics, and contains both activities and didactic lessons. These topics are discussed at the individual, family and school/community level, allowing families to discuss barriers as well as facilitators unique to their rural schools and communities. The sessions begin with a review of progress since the last meeting, and end with parents and children setting goals. Parents and children will work together throughout each session, and both will be required to attend for the entire meeting.

Families will also be asked to complete their homework assignments with intervention staff via the iPad interactive televideo technology. This work will focus on goal setting, problem solving of barriers, reinforcement for tracking, and on completion of assigned homework assignments that are part of the manual. We will provide 11 hours of remote homework assistance to each family using the iPad interactive technology. We determined the 11 hour time period because 14 hours

of regular sessions plus 11 hours of homework assistance puts our intervention at the 25 hour threshold of contact hours set by the USPSTF (we will also have homework for each session, which will ensure that participants get the 25 hours recommended). The USPSTF suggests that

Table 5. Intervention Timeline (25 contact hours total per USPSTF guidelines).										

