Following completion of all baseline measures (which will take one hour; see Measures below), iAmHealthy families will receive their technology devices via postal service and will be scheduled for a 30-minute phone orientation session to all technology. Intervention components will then be implemented for iAmHealthy or newsletter. Weight and height measurements will be taken at each child's school at the start of the intervention and monthly throughout the intervention period for both parents and children by onsite trained staff. Parents or children may have their weight taken at a local hospital or clinic if a medical specialty scale is needed, such as a wheelchair scale or a high-capacity scale. In the event schools are closed (ie. COVID-19 outbreak), parents will be trained on how to obtain height and weight at home. Digital scales and tape measures will be sent to the families, and each family will measure the height and weight during a video call via Zoom app with an iAmHealthy team member to ensure measurement accuracy. At the completion of the intervention (8 months later), the second one-hour measures collection will take place. Sixteen months following the end of the intervention, the third one-hour measures collection will take place (20-month follow-up).

Families from the intervention/control study will be paid proportionally for completion of measures as is required by our local IRB (\$80 at baseline, 8 months, and 20 months, plus \$100 for monthly heights and weights over 10 time points). Participants who wear the activity monitors for at least 7 days will receive an extra \$20 at baseline, 8 months, and 20 months. Altogether, families may receive up to \$400. A payment timeline for participants is attached below:

	Start of Study	1 Month	2 Month	3 Month	4 Month	5 Month	6 Month	7 Month	8 Month	20 Month	Total for Study Completion
Online Surveys	\$80								\$80	\$80	

Height & Weight	\$10	\$10	\$10	\$10	\$10	\$10	\$10	\$10	\$10	\$10	
Activity Monitors	\$20								\$20	\$20	
Total	\$110	\$10	\$10	\$10	\$10	\$10	\$10	\$10	\$110	\$110	\$400

In case of activity monitor malfunction, we would like to be able to offer an additional \$20 for the participant to wear the device again. Thus, a participant could earn over \$400 if they are asked to wear the monitor a 2nd time.

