In case parents or children need to be weighed on a medical specialty scale at another location (local hospital or clinic), we would like to be able to offer an additional \$10 each timepoint for the participant's time in collecting the measurement at another location. If this is the case, a participant could earn over \$400.

In the event schools are closed (ie. COVID-19 outbreak), participants will receive an additional \$10 for each completed study measure, up to an additional \$100. If this is the case, a participant could earn over \$400. Participants will be informed of this change over the phone, and not asked to come into the school to be reconsented.

The onsite school representative will be paid for their services to the study outside of normal school hours/duties (\$30/hr, up to \$2000 per completed site). If the onsite school representative leaves employment with the school, they will be replaced by another suitable school employee selected by the principal. Schools will also be allowed to retain the scales and stadiometers provided by the study, although participants will be required to return all technology equipment, including the iPads.

D. Data Collection

Measures will be completed through REDCap, a secure, web-based application designed exclusively to support data capture for research studies, just prior to the start of the intervention (**baseline**), immediately following the 8-month intervention (**8 months**), and 16 months after the end of the intervention (**20 months**), with the exception of parent and child weight, which will be taken at these time points as well as monthly throughout the 8 month intervention time period. See Table 6 for the Measures Timeline.

Primary Measures

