- 2. Child Body Mass Index z score (BMIz) and Parent Body Mass Index (BMI). To calculate child BMIzand parent BMI we will use standard formulas/equations. Height and weight will be assessed by fully trained onsite school representatives on standardized, calibrated equipment provided by the study. All staff will be trained in standard research anthropometric measurement protocol, including calibration techniques. Standing height will be assessed in

Table 6. Measures timeline.			
Primary Outcome Measures	Baseline	8 months	24 months
24 hour food recall (child)	Х	Х	Х
Physical Activity Monitors (child)	Х	Х	Х
Child BMIz/ Parent BMI ¹	Х	X	Х
R each			
Participation	Х	Х	
Structured Interviews with Non- participants		Х	
E fficacy			
HRQOL (parent, child)	Х	Х	Х
Parent Distress (parent)	Х	Х	Х
Peer Victimization (child)	X	Х	X
Child Depression (child)	Х	Х	х
Satisfaction (parent, child)		х	
Stigma (parent, child)		Х	
A doption			
Assess Representativeness of Participating Schools	Х		
I mplementation			
Attendance/Participation		Х	
Cost		Х	
Group Process		Х	
M aintenance			
Structured Interviews With Participating Schools		Х	
Other Measures			
Demographics (parent)	Х		
Food Insecurity	Х		
Post Questionnaire (parent)		Х	
Technology Feasibility (parent)	Х	Х	
$^{1}\mbox{Child BMIZ/Parent BMI will be taken monthly throughout}$	the 8 month into	ervention period	

triplicate via a Harpenden Holtain stadiometer, Model 603 (Holtain, Crymych, UK). Weight will be measured in triplicate on a portable SECA digital scale (SECA, Hamburg, Germany) after the participant has been asked to void. Parents and children will be measured with light clothing and no shoes.

Other Measures

1. *Demographics*. This questionnaire will ask about age, race, ethnicity, income, free/reduced lunch status, and parental education. We will also assess for the availability of home computers, high-speed internet access, tablets, smartphones, or other technology already present in the home that could be utilized for secure videoconference

- connections in future studies.

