- they already own (such as a FitBit). We will ask them to share their data with the iAmHealthy FitBit or Garmin accounts. The health coach will then be able to see the parent and child's daily steps and give them feedback during their 1-on-1 health coaching calls. The data will be retained as part of the study database and used for analysis. Parents and children may keep the pedometer after the study ends.
- 7. *Maintenance.* The study team will conduct structured interviews with participating schools to assess their ability to sustain key components of the iAmHealthy intervention over time. This will include reflections on key factors associated with long-term maintenance of behavior change by participating families, but also key factors at the school/organizational level in regard to their ability to implement and maintain iAmHealthy, focusing in detail on which aspects of the program were maintained and how these specific factors were maintained.

E. Statistical analyses.

Quantitative Analysis. In order to address the Aims, both Intent-to-Treat (ITT) analyses and analyses of completers are proposed. The ITT analysis is necessary as we predict that at least some participants will withdraw prior to the completion and compares those randomized to each of the treatment conditions. Any participant who consents to participate, completes all baseline measures, and has at least one measurement after baseline will be included in the intent-to-treat analyses. Since monthly assessments are done on weight and height for intervention purposes, we will have parent and child outcome data available for use in the intent-to-treat analysis for the secondary hypothesis variable of BMIz and several of the other variables to address questions of intervention effectiveness through the 8-month intervention period. The second is an efficacy analysis for those who are identified as completers of the intervention. A completer will be defined as a participant who receives at least 80% of their assigned intervention. For those in the comparison group, the criteria will be 80% of their data collection time points. The analysis approach will be the same for both efficacy and intent-to-treat analyses; only the participants and scores included will vary.

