Some outcomes will be analyzed using the multilevel model described above with a baseline covariate. These outcomes include Efficacy outcomes for parent and child reports of HRQOL, parent distress, child depression, and child peer victimization. A second set of outcomes involve tests of treatment condition differences where a baseline covariate is not available. These outcomes will be analyzed similarly with a multilevel model, however there will not be a level-1 covariate for the outcome at baseline. Outcomes to be analyzed in this manner include: parent and child satisfaction within Efficacy as well as attendance, participation, and cost from Implementation. The stigma outcome within Efficacy will be analyzed by comparing the proportions reporting child stigmatization between treatment conditions. This will be done for both child and parent report. A third set of outcomes will be examined descriptively. These outcomes include participation from Reach as well as descriptions of the barriers obtained in the qualitative analysis, school-level demographics from Adoption, engagement from Implementation, the number of schools retaining intervention components and summaries of factors related to maintenance from Maintenance. Participant demographics, reported food insecurities, and technological feasibility will also be examined descriptively.

Missing Data. While attrition and incomplete data may be unavoidable, the deleterious effects missing data may have on our results can be mitigated through a combination of careful data collection and thoughtful analysis. Full information maximum likelihood estimation which uses all available data to build a multidimensional likelihood function for each highest-level unit (schools) will be used for the multilevel models. For variables brought into the likelihood function, any missing cases are assumed missing at random, which means random only after conditioning on model predictors and the observed outcomes. Reasons for student departure (e.g., dropout versus changing schools) can be tracked and included as model predictors to help reduce the bias that might otherwise be created.

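### The school Maintenance interview is scheduled only at 8 months, when the intervention ends, so the planned count of schools retaining components cannot measure retention

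*Combined protocol and SAP*

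**What the plan says.** Item 7 (Maintenance) of Other Variables Assessed, in Section II.D, says that schools will be interviewed "to assess their ability to sustain key components of the iAmHealthy intervention over time". The content is partly about capacity, namely "key factors at the school/organizational level in regard to their ability to implement and maintain iAmHealthy", and partly retrospective, "focusing in detail on which aspects of the program were maintained and how these specific factors were maintained". The item gives no interview date.

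The date comes from Table 6. Under Maintenance the table has one row, "Structured Interviews With Participating Schools", with a single mark in the 8-month column and none at baseline or at the last follow-up. The opening paragraph of Section II.D defines the 8-month assessment as "immediately following the 8-month intervention", and Section II.A describes sessions running "for a total intervention period of 8 months".

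Section II.E places Maintenance among the outcomes to be examined descriptively and names two outputs: "the number of schools retaining intervention components and summaries of factors related to maintenance from Maintenance". Nowhere do the documents schedule a later school interview.

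**The concern.** Retention means that something continues after the support for it has stopped. Up to month 8 the study is itself active at the school: Section II.C has onsite staff measuring height and weight every month, and pays the school representative for study work. An interview held as that period closes can ask what is in place on that day, or what the school expects to keep. It cannot ask what the school kept.

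The school interview is the only measure that Table 6 lists under Maintenance. If the schedule is followed and the result is reported under the Section II.E wording, readers will take a statement about status or plans as evidence that schools carried components forward.

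**Working it through.** No sample size, power or alpha figure is involved, and the plan gives no figure of its own to reproduce. The check is a reading of the schedule against the text, plus a subtraction.

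**Inputs**
- Interview time: month 8 (Table 6, Maintenance row).
- End of intervention: month 8 (Section II.A). Table 5 shows the last session block as weeks 29-32.
- Last follow-up: labelled 20 months in Sections II.C and II.D, but also described there as 16 months after the intervention ends. Table 6 labels it 24 months.

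**Post-intervention time = interview month − month in which the intervention ends**
- As scheduled: 8 − 8 = 0 months.
- Counting from the last week in Table 5: 8 months × 4.35 weeks per month = 34.8 weeks, and 34.8 − 32 = 2.8 weeks, so about 3 weeks at most.
- At the last follow-up, if it is at 20 months: 20 − 8 = 12 months.
- At the last follow-up, if it is at 24 months: 24 − 8 = 16 months. This agrees with the 16-month description, since 8 + 16 = 24.

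**Which content needs elapsed time**

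| Content | Section | Can be collected at 8 months? |
|---|---|---|
| Perceived ability to sustain components | II.D, item 7 | Yes, as a prospective view |
| School-level factors in implementing and maintaining the program | II.D, item 7 | Yes |
| Summaries of factors related to maintenance | II.E | Yes, as perceived factors |
| Which aspects were maintained, and how | II.D, item 7 | No |
| Number of schools retaining components | II.E | No |

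**Reliability of the table reading.** Table 6 was read from PDF. The layout of the Maintenance row matches other rows marked only at 8 months, such as Satisfaction and Cost, so a misplaced mark is unlikely.

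**The case against.** The best defence is that much of the Maintenance item is about capacity. Schools can say at 8 months what helped, what got in the way and whether they think they could continue, while delivery is still fresh. That stands. A reader might infer from the schedule that Maintenance cannot be assessed at all; the documents do not support this, because the factor summaries remain obtainable. Table 6 also marks diet recall, activity monitoring and BMI measures at the last follow-up, so persistence in families is measured. That narrows the gap, but says nothing about what schools kept.

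Item 7 sets no date, so this is a mismatch between Table 6 and the text and not an explicit decision against later contact. That too is fair, but staff working from the schedule would interview at 8 months only.

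Two further inferences are tempting. One is that newsletter schools, perhaps half of the 18, would sit in the denominator with nothing to retain. Section II.E states a count with no denominator, equal allocation is not stated, and item 7 ties the interview to the iAmHealthy intervention. Section II.A also describes training randomised schools in intervention procedures without separating the arms. Loose wording about which schools are counted is a reason to clarify, not a measurable error. The other is that the count is bound to overstate sustainability. That direction is plausible, but the interview questions are not in the documents and no figure there supports the size or certainty of a bias.

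Finally, simply moving the interview would lose fresh information on implementation and rely on recall a year or more later. That objection is sound and shapes the fix.

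**Conclusion.** The point holds in a limited form. With about 0 months (at most about 3 weeks) of post-intervention time at the only scheduled school interview, the planned count cannot measure retention, and the retrospective questions cannot be answered as worded. The perceived-ability and factor content is unaffected.

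This rests on Table 6 being the operative schedule and on no later school contact being planned elsewhere; none appears in the documents. It does not depend on the allocation ratio or on any assumed bias. The consequence is modest: the outcome is descriptive, with no hypothesis test and no bearing on the primary comparison. It is still worth correcting, because it decides whether the trial can say anything about school-level retention.

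**What to change.** 1. In Table 6, add a mark for the school interview at the existing last follow-up and ask the retention question there. First reconcile that visit's label across Sections II.C and II.D and Table 6, so that the interval is known to be 12 or 16 months.
2. Keep the 8-month interview for implementation factors and perceived ability to sustain the program.
3. In Section II.E, state that the retention count refers to schools randomised to iAmHealthy, and that it is taken from the late interview.
4. If no late interview is done, report the 8-month result as intended or perceived sustainability, and drop the retention wording.

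**Cost.** One short extra contact per iAmHealthy school, which is fewer than the 18 schools in total. The last follow-up already exists, and Table 6 marks height- and weight-based measures there. Some school contacts will have changed by then. Section II.C provides for replacing a representative who leaves, but a replacement may not have seen the program delivered, which is a further reason to keep the 8-month interview. The sponsor would also need to list which school-level components count as retained, since the documents do not name them and the sessions themselves are delivered to homes. Option 4 costs only a change of label.

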 of children who express interest in the program divided by the total number of children eligible. Percent enrolled
 will be calculated as the total number of children who complete enrollment procedures divided by the total number
 of children who expressed interest.
- 2. *Adoption.* Adoption will be measured by calculating the representativeness of the participating schools. Specifically, participating schools will be measured on their student body size and their percent free/reduced lunch and will be compared as a group to the overall data that is available for all elementary schools in the state of Kansas on these key variables to assess for the representativeness of participating schools.
- 3. Attendance and Participation. Percent attendance will be calculated for each parent/child pair as the percent of sessions attended divided by the total number of sessions offered. Participation will be assessed for both groups by asking the parents and children about additional health related information they sought to supplement the content of the program, such as health websites, apps, books, programs, etc. For both groups participation will also include the amount of homework that was completed from the sessions (as a percent) self-reported as part of the Post Questionnaire at the 8-month time point.
- 4. *Cost.* Cost will be analyzed in terms of cost effectiveness, defined as cost per unit change in BMIz, by our experienced health economist ([name]). The cost perspective will be societal, meaning that both provider and client costs will be measured.⁵⁰
- 5. *Group Process Factors.* In order to assess factors related to the group process for the iAmHealthy intervention, as well as to assess for engagement in the group sessions, we will use the Living in Familial Environments Coding System. ^{55,56} Per proper procedures, only initial sessions will be coded for the 15 content codes (facilitative, solicitous, self-positive, problem statement, proposed solution, complaint, oppositional, command unaccountable, self-complaint) which fall into 3 categories (positive, negative, neutral). This coding will be completed for each parent and child separately and allow for a calculation of child engagement and parent engagement uniquely.
- 6. *Pedometer Steps.* Both parents and children in the intervention group will be asked to track their steps throughout the study. We will provide Garmin Vivofit devices to parents and children, or the family may choose to use a device

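### The intent-to-treat set is narrower than the comparison it is said to make, and the completer efficacy analysis selects the two arms on different behaviours

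*Combined protocol and SAP*

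**What the plan says.** Section II.E (Quantitative Analysis) of the combined protocol and SAP proposes two analyses with the same model and different participants.

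- **ITT.** This analysis, it says, "compares those randomized to each of the treatment conditions". Membership is then limited to a consenting participant who "completes all baseline measures, and has at least one measurement after baseline will be included in the intent-to-treat analyses". Which later measurement counts is not stated.
- **Completers.** "The second is an efficacy analysis for those who are identified as completers of the intervention". For iAmHealthy, "A completer will be defined as a participant who receives at least 80% of their assigned intervention". For controls, "For those in the comparison group, the criteria will be 80% of their data collection time points".

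The Missing Data paragraph of II.E adds full information maximum likelihood (FIML) under a missing-at-random assumption. Neither analysis is named as primary.

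**The concern.** An analysis of those randomised and an analysis of those with a full baseline battery and a later value are different populations. Table 6 lists many unrelated baseline instruments: diet recall, activity monitor, quality of life, parent distress, peer victimisation, child depression, food insecurity. As worded, a missing parent questionnaire removes a child with complete monthly BMIz data from the BMIz analysis. If that happens to any enrolled child, a modified ITT is reported as ITT and usable data are discarded.

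The completer comparison has a different fault. One arm is selected on taking up the intervention, the other on turning up to be measured. Both happen after allocation, and they are not the same behaviour, so randomisation does not protect the contrast. A difference between completers could come from the selection rules alone and still be reported as efficacy.

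**Working it through.** **The plan's own figure.** II.B gives 8 pairs at 18 schools: 18 × 8 = 144, as stated. With 175 consented, 1 − 144/175 = 17.7% are expected to be lost between consent and enrolment. The documents give no dropout rate, ICC or SD, so every rate below is an assumption.

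**1. Who can fall out of the ITT set.**
- In II.C, height and weight are taken after consent to confirm eligibility, and intervention components start after baseline. If baseline completion gates enrolment, 0 of 144 are lost.
- If 2% of enrolled children miss an instrument: 144 × 0.02 = 2.9, about 3.
- If the battery includes a valid monitor week and 10% fail it: 144 × 0.10 = 14.4, about 14. This reading is less likely, because II.D has its own 4-of-7-day rule for the monitor and II.C pays for re-wear after malfunction.
- Precision: SE = √[(4/n)(1 + (m − 1)ICC)], with m = n/18 and ICC 0.01 to 0.05. At n = 144 it is 0.172 to 0.194 SD. It rises by about 1% at n = 141 and by 4 to 5% at n = 130.
- The later-measurement condition is easily met for BMIz, which is measured monthly. Diet and activity are measured after baseline only at 8 months and the final follow-up, so one monthly weight could admit a child with no later value of those outcomes. Loss under this condition can differ by arm whether baseline comes before or after allocation.

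**2. What each 80% means.**
- iAmHealthy by sessions: 8 weekly + 6 monthly = 14 (Table 5); 0.8 × 14 = 11.2, so 12.
- iAmHealthy by contact hours: in II.A, 14 hours "of regular sessions plus 11 hours of homework assistance puts our intervention at the 25 hour threshold of contact hours", so 25; 0.8 × 25 = 20.
- These disagree. All 14 one-hour sessions with no homework help is 100% of sessions but 14/25 = 56% of hours. Nine sessions plus 11 homework hours is 9/14 = 64% of sessions but 20/25 = 80% of hours.
- Makeup calls: "If a participating family misses one group session, they will receive a makeup phone call". Whether the call counts is not stated.
- Comparison arm: 0.8 × 10 height/weight points = 8; 0.8 × 9 points through month 8 = 7.2, so 8; 0.8 × 3 main assessments = 2.4, so 3. A family measured from the start to month 7 has 8/10 and is a completer with no 8-month or final value, but has 1 of 3 main assessments.

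**3. Completer difference with no true effect.** Let completion be a threshold on a normal latent trait with correlation ρ to outcome. Among a kept share p, the trait mean is λ(p) = φ(z)/p, where z is the cut-off: λ(0.6) = 0.644, λ(0.7) = 0.497, λ(0.8) = 0.350, λ(0.9) = 0.195. The unadjusted difference, iAmHealthy minus comparison, is ρ[λ(p₁) − λ(p₂)]. A positive value favours iAmHealthy if more engaged families do better.
- 60% versus 90% kept: 0.449 × 0.1 to 0.3 = 0.045 to 0.135 SD.
- 80% versus 90%: 0.155 × 0.1 to 0.3 = about 0.02 to 0.05 SD.
- 90% versus 70%: −0.302 × 0.1 to 0.3 = −0.030 to −0.091 SD.
- Equal 60% shares, but ρ = 0.3 in one arm and 0.1 in the other because the behaviours differ: 0.2 × 0.644 = 0.129 SD.

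**4. With a baseline covariate.** Let r be the baseline-outcome correlation and ρ₀ the completion-baseline correlation. The adjusted difference is approximately (ρ − rρ₀)[λ(p₁) − λ(p₂)]. For 60/90:
- ρ = 0.3, ρ₀ = 0: 0.3 × 0.449 = 0.135 (simulated, r = 0.5: 0.134).
- ρ = 0.3, ρ₀ = 0.24, r = 0.8: 0.108 × 0.449 = 0.048 (simulated 0.049).
- ρ = 0.3, ρ₀ = 0.375, r = 0.8: 0.3 − 0.8 × 0.375 = 0, so no bias. The same holds at ρ = 0.1, ρ₀ = 0.125.

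**5. Scale.** With 72 per arm, 60% and 90% leave 43.2 + 64.8 = 108, or m = 108/18 = 6 per school. The unadjusted SE is √[(1/43.2 + 1/64.8)(1 + 5 × ICC)] = 0.201 at ICC 0.01 and 0.220 at ICC 0.05. The largest unadjusted artefact, 0.135 SD, is therefore about 0.6 to 0.7 of one SE.

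**The case against.** The strongest reply on the ITT set is that the rule may exclude nobody. Eligibility height and weight, baseline before intervention, and 175 consented for 144 enrolled all fit a reading in which only children with a full baseline become participants. That stands as a natural reading and limits the point. It does not remove it, because no section says that enrolment requires every instrument.

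A reader might go further and infer that baseline loss differs by arm because II.A sends study scales only after schools are randomised. Baseline height and weight do appear to follow allocation. But II.A also has families signing up before their school is assigned, and no section gives the order for the other instruments or says whether families then know their arm. Differential baseline loss is not shown.

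On completers, the reply is that controls appear to receive a newsletter and so have no sessions to count, which makes some asymmetry unavoidable. II.C supports that, although II.D refers to session homework in both groups and II.E compares attendance between conditions. An unavoidable asymmetry is a reason not to call the contrast efficacy; it does not make the arms comparable.

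It is also fair that II.D already points to sessions: "Percent attendance will be calculated for each parent/child pair as the percent of sessions attended divided by the total number of sessions offered". Contact hours received are not a listed measure. What is missing for iAmHealthy is a cross-reference, and the open denominators alone would be a minor clarification. Finally, baseline adjustment can remove the completer bias altogether, as step 4 shows.

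**Conclusion.** The point holds as a fault in two stated rules and should be fixed. The ITT label and the ITT membership rule conflict, and FIML cannot repair this because it uses only children in the set. The completer rules select the arms on different post-allocation behaviours, so the contrast is not an efficacy comparison. Neither conclusion depends on an assumed rate.

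The sizes do. Baseline exclusions may be zero. With 60% versus 90% kept and completion-outcome correlation 0.1 to 0.3, the completer artefact is 0.045 to 0.135 SD unadjusted and 0 to about 0.13 SD adjusted, under one SE in either case. Other retention patterns reverse the sign.

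A reader might infer that the ITT estimate is biased, or that the completer result must favour iAmHealthy. The documents support neither: they give no rates by arm, and the completer analysis sits beside the ITT analysis without altering it. II.E also refers back to a multilevel model whose description is not in the text available, so some analysis detail may be unseen.

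**What to change.** 1. **ITT set.** Define it as every enrolled eligible child in a randomised school, analysed in the school's assigned arm, without requiring unrelated baseline instruments or a later measurement. Bring the baseline value of the analysed outcome into the FIML likelihood so that a child missing it is kept. Retain the present set as a sensitivity analysis labelled modified ITT. Enrolment procedures need not change.
2. **Completers.** Label the comparison supportive and non-randomised, and draw no efficacy conclusion from it.
3. **Minor clarification, before analysis.** Tie the iAmHealthy 80% to sessions attended over sessions offered, as II.D already defines attendance, and say whether makeup calls count. Name the comparison-arm schedule: 10 height/weight points, 9 through month 8, or 3 main assessments.

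The cost is SAP wording and slightly more modelling, with no new data. The completer result will carry less weight.
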